2. ANALYSIS PLAN

2.1 Primary analysis

The primary outcome will be analyzed as intention-to-treat (ITT). The number of episodes per week among the active case detection (ACD) cohort (children age ≤ 10 years) will be used as the primary measurable outcome to evaluate the impact of the intervention when compared to the control arm. The active case detection cohort includes all enrolled children regardless of

eligibility or receipt of MDA or SMC. A mixed effects regression analysis with Poisson distribution will be used to assess the impact. The primary analysis will include a random effect for cluster (village), and 3 fixed effects (treatment effect, year, and sex; all binary covariates, no interactions evaluated). Subgroup analyses will include an evaluation of fixed effects such as LLIN use, age, and treatment with SMC or IVM. Estimates for the intervention effect from the primary analysis as well as subgroup analyses will be reported along with 95% confidence intervals. The statistical program SAS v9.4 (SAS Institute Inc., Cary, NC) will be used for primary statistical analyses. Secondary data generated from Aim 1 will include adverse events (AE), severe adverse events (SAE), and their relationship to the intervention/placebo. The risk of SAE and AE will be compared between intervention and control arms by calculating risks ratios and attributable risks with 95% confidence intervals.

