## 2.2. Rationale

Malaria is a major cause of morbidity and mortality in Burkina Faso; it has some of the highest transmission intensities in the world, as assessed by the entomological inoculation rate (<http://www.map.ox.ac.uk/>), and there has been limited decrease in endemicity of the disease that has been observed in other SSA countries (30). The most prevalent species of parasite is *Plasmodium falciparum*, with less than 20% being *Plasmodium malariae* or *P. ovale* (31). A high proportion of persons living in rural, underdeveloped villages in endemic areas are infected with the malaria parasites throughout the year, but transmission is highly seasonal, beginning with the onset of the rainy season

---

and a subsequent dramatic increase of the malaria vector population (32). As such, the burden of overt clinical disease is on children  $\leq$  5 years of age who have not developed adequate immunity. In the southwest, clinical incidence is between 2-4 episodes per child per year (33). Clinical incidence in this age stratum spikes at the onset of the rainy season, likely due to a sharp increase in transmission events of new parasite clones accompanying the rise in mosquito populations at the start of rains (34).

Treatment options are limited to frontline ACTs because of a high prevalence of resistance to older antimalarials such as sulfadoxine-pyrimethamine (SP), chloroquine (CQ), and amodiaquine (AQ) (32). Current National Malaria Control Program (NMCP) recommends either AL or artesunate plus AQ (ASAQ) as first-line for the treatment of malaria in Burkina Faso. Due to prevalent infections, especially in rural, underdeveloped areas, the NMCP policy is to only treat symptomatic cases of malaria to limit drug resistance to the first-line ACTs. Outside of anti-malarial treatment, most malaria control is achieved through vector control. LLINs are the primary tools employed for limiting vector contact with humans and reducing the vector population through the impregnated insecticides in the nets (pyrethroid insecticides). To a lesser extent, IRS operations using pyrethroid and carbamate insecticide classes are performed in some areas. Unfortunately, mosquito resistance to both of these insecticides is widespread, partially due to their widespread application in agricultural operations that are prevalent in the same afflicted villages, especially cotton and rice production (35). New tools will be critical to achieving malaria control in the country.

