**Table 3: Summary of the study groups and schedule for blood sampling.**

Group	Number to sample	Ages	What and when samples collected				
			BS=blood smear FP=filter paper	BS&FP -when malaria diagnosed	BS&FP -before season	BS&FP -between the second and third MDA each season	BS&FP -dry season/ post intervention (only from select participants)
Child cohort (followed with active case surveillance)	~1800	≤10 yr. olds	BS&FP -when malaria diagnosed	BS&FP -before season	BS&FP -between the second and third MDA each season	BS&FP -post season	BS&FP -dry season/ post intervention (only from select participants)
Households# on village transects (3 villages/arm; ~8 households/village)	~380	all note: ≤10 yr. olds will be sampled in the ACD cohort		BS&FP -before season	BS&FP -between the second and third MDA each season	BS&FP -post season	BS&FP -dry season/ post intervention
PK-PD modeling cohort	180	5-10yo (n=30 per arm) 11-18yo (n=30 per arm) ≥19yo (n=30 per arm)	Each participant sampled for capillary blood up to 5 of the following time points after their last dose of IVM: 0h (pre-last dose), 1h, 4h*, 8h, 12h*, 24h, 48h, 52h, 60h, 72h, 7d*, 14d, 21d and 28d. *venous blood will be collected simultaneously at these time points				

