## 10.2. Sample Size Considerations

[figure not shown]
The trial design and power calculation is guided by the Malaria Transmission model developed at Imperial College, London (<http://www.imperial.ac.uk/malaria-modelling/tools-and-data/>) and informed by data from our RIMDAMAL I trial as well as the longer mosquitocidal effect (up to 30 days) from the intervention dose and regimen predicted from IVERMAL data. The model suggests we should observe an effect size in the intervention arm over the control arm of 43.1% (Figure 4). This assumes a rate incidence in our 0-10 yr. old cohort of 1.088 malaria episodes/child/year and 0.619 malaria episodes/child/year in the control and intervention arms, respectively. To determine the cluster sample size and cluster population (children cohort size) we used the sample size formula for obtaining the number of clusters in an unmatched CRT design with a 'rate' endpoint (49). The formula uses the coefficient of variation ( $\kappa$ ; SD/mean) of the true rates between clusters within each group, which we estimated in southwestern Burkina Faso to be 0.258 (50). From these variables, and setting the  $\alpha=0.05$  (Type I error rate or probability of detecting a false negative result = 1.96), 6 clusters/arm with a minimum of 48 children/cluster in our child cohort is necessary to detect a significant difference in the rates between the arms with 80% power (Type II error rate or probability of rejecting a false positive result = 0.84). Relatedly, if we instead calculate the cluster population sample size using the intraclass correlation coefficient retrospectively calculated from RIMDAMAL I data (ICC=0.059), and setting the  $\alpha=0.05$ , with 6 clusters/arm the necessary number of children to follow per cluster is 9.

In January 2019, the sample size modeling exercise was re-performed because it was learned that that villages in the Diebougou health district (the study site) were expected to receive new Interceptor G2 LLINs prior to the 2019 rainy season. These new LLINs are made with two different insecticides (chlorphenapyr and alpha-cypermethrin) to circumvent the prevalent pyrethroid-resistance seen in Burkina Faso the much of SSA. Thus, we assumed a 12%-50% reduction in malaria incidence in

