both arms due to distribution of these nets. Keeping with an effect size of 43.1% in the intervention arm over the control arm, using an intra-cluster coefficient of 0.2, and increasing the sample size to 100 children/cluster in our child cohort, we need between 4.9 and 5.5 clusters/arm to detect a significant difference in the rates between the arms with 80% power. Given that we will select 7 villages per arm, which are expected to have population sizes of 0-10 year old children of approximately 100, we feel we will have >80% power to reject the null hypothesis if it is false, even if some children drop out of the study or are lost to follow-up.

The primary outcome will be analyzed as intention-to-treat. The incidence of episodes from the children cohort will be used as the primary measurable outcome to evaluate the impact of the intervention when compared to the control arm. The primary analysis will use either cluster-level analyses, or multilevel/hierarchical regression modeling techniques to account for clustering at the level of the randomization unit (village), as well as analyze individuals with multiple time points. and comparisons using a critical value of  $\alpha$  at 0.05. The analysis may need to be corrected to account for the relatively few number of clusters in the study design. The unadjusted as well as adjusted estimates depicting the impact of the intervention versus control will be reported along with 95% confidence intervals. The statistical programs R (r-project.org), SAS v9.4 (SAS Institute Inc., Cary, NC), or others will be used for the primary statistical analyses.

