- 6. Important medical events that may not result in death, be life-threatening, or require hospitalizations may be considered serious when, based upon appropriate medical judgment they may jeopardize the patient or subject and may require medical or surgical intervention to prevent one of the outcomes listed in this definition. Examples of such medical events include allergic reaction requiring intensive treatment in an emergency room or at home, blood dyscrasias or convulsions that do not result in inpatient hospitalization, or the development of drug dependency or drug abuse.

ii. Severity (grade)

- Grade 1 (mild)
- Grade 2 (moderate)
- Grade 3 (severe)
- Grade 4 (potentially life-threatening)
- Grade 5 (death)

iii. Outcome

- recovered/resolved without sequelae (grade for the event returned to <2)
- recovering/resolving (grade for event is decreasing and not greater than 2)
- not recovered/not resolving (adverse event still present but stable)
- recovered/resolved with sequelae (grade for the event returned to <2, however some pathological condition resulting from a disease, injury, or other trauma)
- Death
- unknown (example for using this code is when a participant is lost to follow up and outcome cannot be determined)
- iv. **By body system and preferred term** using MedDRA coding (27 groups)

2.2.2 Parasitological secondary endpoints and analysis.

The following are key secondary parasitological endpoints, and the method of analysis will depend on the type of data collected:

- Parasite prevalence. Parasite prevalence of *Plasmodium falciparum* will be assessed either by:
 - molecular assay (PCR-based off of filter paper from capillary finger-prick samples). Filter paper samples are obtained at the beginning and end of each intervention season, and monthly, prior to each MDA in the ACD cohort. In addition, filter paper was obtained in the entire cohort at the beginning and end of the 2020 intervention season.
 - blood smear (only for ACD children at the time of diagnosed malaria infection by RDT)
- Multiplicity of infection (MOI, also sometimes referred to as complexity of infection (COI). This is defined as the number of unique clones per individual at the time of diagnosis of malaria infection (count data). It is based either on microsatellite typing or amplicon sequencing

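### The primary model adjusts for sex and year but for neither child age nor village baseline parasite prevalence, although most of the uncertainty lies between villages and the 7 v 7 draw is unrestricted

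*SAP*

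**What the plan says.** The primary model in SAP 2.1 contains "3 fixed effects (treatment effect, year, and sex; all binary covariates, no interactions evaluated", with a random effect for village. The GLIMMIX code in SAP 2.1.3 matches: treatment, year and sex, a log person-week offset, a random village intercept and Kenward-Roger degrees of freedom.

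Age is placed elsewhere: "Subgroup analyses will include an evaluation of fixed effects such as LLIN use, age, and treatment with SMC or IVM". Protocol 10.2 promises more than one analysis, "The unadjusted as well as adjusted estimates depicting the impact of the intervention versus control will be reported", but names no covariates.

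Baseline parasite samples are planned. SAP 2.2.2 states "Filter paper samples are obtained at the beginning and end of each intervention season, and monthly, prior to each MDA in the ACD cohort", and the sampling schedule in Protocol Table 3 lists "BS&FP -before season" for the child cohort.

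Protocol 5.3.1 allocates villages by drawing 14 sealed envelopes, seven per arm. No stratification, matching or restriction is described.

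**The concern.** With 14 villages, the precision of the arm contrast depends mainly on how much transmission differs between villages. The two adjustment covariates say little about that. Both seasons are observed in every village, and the sex ratio among children up to 10 should be similar everywhere.

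A simple draw of seven against seven can place the higher-transmission villages mostly in one arm. The primary model would then have nothing with which to correct for it. If the imbalance were noticed only after unblinding, an adjusted analysis chosen at that point would look data-driven. The trial already holds a village-level measure of transmission taken before treatment, and it records every child's age.

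**Working it through.** **Inputs.** Rates 1.088 and 0.619 (rate ratio 0.569), from Protocol 10.2 and SAP 1.3. Between-village coefficient of variation κ: the protocol describes it as one "which we estimated in southwestern Burkina Faso to be 0.258" for the initial 6 × 48 design, and uses 0.2 in the January 2019 revision with 100 children per village. Net effect: incidence 12–50% lower in both arms (Protocol 10.2). Final design: 7 villages per arm, about 100 children each, two seasons (SAP 1.3).

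**Reproducing the plan's figures.** Clusters per arm: c = 1 + (1.96 + 0.84)² × [(λ0 + λ1)/y + κ²(λ0² + λ1²)] / (λ0 − λ1)². With κ = 0.258 and y = 48: c = 1 + 7.84 × (0.0356 + 0.1043)/0.2200 = 5.99, the stated 6 per arm. The plan therefore counts one rate-year per child. The revised range of 4.9 to 5.5 comes out as 4.93 to 5.46 if 0.2 is read as κ and the additive constant is 2. With a constant of 1 it would be 3.93 to 4.46.

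**Between-village share of the variance.** Share = κ²(λ0² + λ1²) / [κ²(λ0² + λ1²) + (λ0 + λ1)/y].

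- κ = 0.258, y = 200 (100 children, two rate-years), no net effect: 0.1043/(0.1043 + 0.0085) = 92%.
- κ = 0.2, y = 200, no net effect: 0.0627/(0.0627 + 0.0085) = 88%.
- κ = 0.2, y = 200, incidence halved by nets: 0.0157/(0.0157 + 0.0043) = 79%.
- If the rates are annual and only 8 months are observed (y = 100 × 8/12 = 66.7): 80% at κ = 0.258 and 71% at κ = 0.2 before any net effect. It falls to 55% in the least favourable case (κ = 0.2, incidence halved).
- From the previous trial's ICC of 0.059 with 100 children: 5.9/(1 + 99 × 0.059) = 86%.

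The κ-based shares treat children within a village as Poisson. Extra variation between children would lower them.

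**Size of a chance imbalance.** The arm difference in mean log village rate has SD = κ√(2/7). That is 0.138 at κ = 0.258, so about 5% of draws give underlying rates differing by 31% or more (exp(1.96 × 0.138) = 1.31), and about 19% give 20% or more. At κ = 0.2 the SD is 0.107, and the figures are 23% or more, and about 9%. The previous trial's risk ratio was 0.80 (Protocol 2.1).

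**Price of a village-level covariate.** One of about 12 degrees of freedom is lost (critical t 2.179 to 2.201). In addition, the covariate is itself imbalanced by chance between 7 and 7 villages, which inflates the expected variance by 1 + 1/(14 − 4) = 1.10. Together: √1.10 × 2.201/2.179 ≈ 1.06.

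**Simulation.** 40,000 trials per cell, village log rates with Poisson counts, 7 v 7, κ = 0.258, y = 200, village-level regression with and without the covariate. Unadjusted power is about 95% at the planned effect and about 64% at a 30% reduction.

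| Assumed correlation of prevalence with village incidence | Mean interval width | Power, planned effect | Power, 30% reduction |
|---|---|---|---|
| 0 | 5.5% wider | 93% | 60% |
| 0.3 | about 1% wider | 94.5% | 63% |
| 0.5 | 7% narrower | 97% | 71% |
| 0.6 | 14% narrower | 98% | 77% |

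Break-even lies at a correlation of about 0.3 to 0.35. With κ = 0.2, unadjusted power at the planned effect is already about 99%.

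**The case against.** The strongest reply is that the pre-specified model is valid as it stands. Leaving out a baseline covariate does not bias a randomised comparison. SAP 1.3 claims over 90% power, and a noncentral-t approximation agrees: 94.7% with two rate-years and 91.1% with 8 calendar months, at κ = 0.258. All of this stands, so the case rests on unlucky draws and smaller effects.

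Nor do the documents give a correlation between baseline prevalence and village incidence. There are reasons for doubt. Protocol 2.2 says a high proportion of villagers carry parasites all year, so prevalence may separate villages poorly. SAP section 3 places the new nets only in 2020, so a season-1 baseline would predate a change in season-2 transmission. This stands too, and it is why the cost of the prevalence term must be stated.

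Age, net use and SMC or ivermectin treatment are already down for subgroup evaluation, and adjusted estimates are promised. But a subgroup evaluation does not put age in the primary model, and the promise names no covariate. SAP 2.1.3 says simulation studies guided the choice of model. That source is not available here, and nothing in the SAP says that baseline village covariates were compared.

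A reader might infer more than the documents support:

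- **That village variation is about 90% of the uncertainty.** This is the upper end. It pairs 0.258 from the initial design with the final village size and two full rate-years.
- **That the protocol ranks age or SMC status as the strongest predictor.** Protocol 2.2 says "the burden of overt clinical disease is on children" aged 5 or under, for want of immunity. It ranks nothing and does not mention SMC status there.
- **That a useless covariate would cost only the lost degree of freedom, about 1% in width.** This ignores chance imbalance in the covariate. The simulated cost is 5.5%.

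**Conclusion.** The concern holds as a matter of efficiency and protection, not validity. Most of the variance of the arm contrast lies between villages in every scenario computed, and neither the draw nor the two adjustment covariates addresses it.

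The two omitted covariates differ in what they offer. Age is already recorded and costs essentially no village-level degrees of freedom. Its gain is modest, because every village seeks to enrol all children up to 10 and age therefore varies mainly within villages. Village prevalence is the covariate aimed at the dominant variance. It pays only if its correlation with village incidence exceeds about 0.3 to 0.35, and no document supplies that figure. At correlations of 0.5 or 0.6, power at a 30% reduction would rise from about 64% to about 71% or 77%. At zero correlation, power at the planned effect would fall from about 95% to 93%. These results assume κ = 0.258, two rate-years and Poisson variation within villages.

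**What to change.** Amend SAP 2.1 and the SAP 2.1.3 code before unblinding.

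1. Add child age at season start (SMC-age v older, or years) as a fixed effect in the primary model.
2. Add village parasite prevalence from the season-1 pre-MDA samples as a continuous village-level term. Use season 1 only, because the season-2 baseline follows four treatment rounds. If the sponsor prefers not to put it in the primary model, name it as the covariate of the adjusted analysis promised in Protocol 10.2.
3. Report the current three-effect model alongside.
4. State in the SAP that the correlation is assumed, and give the possible loss as well as the possible gain.
5. Define the prevalence measure. Protocol Table 3 lists smear and filter paper before the season, whereas SAP 2.2.2 confines smears to diagnosed episodes, so the value may have to come from PCR. State also that newborns and other children who join later do not contribute to their village's value.

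The cost is SAP wording and, for prevalence, one village-level degree of freedom plus the risk of the wider interval described above. The season-1 baseline samples must be read before the primary analysis, which is laboratory work and not only drafting. If the data have already been unblinded, the adjusted model should be labelled post hoc.

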## 5.2. Subject Exclusion Criteria

Exclusion criteria for participating in the intervention (IVM/placebo MDA):

- Residence outside of the study village
- Height < 90 cm (\*note: if subject becomes ≥90cm over course the trial, this exclusion criteria will no longer be valid in subsequent MDA)
- Current treatment with SP+AQ as part of SMC (restricted to children 3-59 months old) (\*note: if subject discontinuous SP+AQ treatment because they become older than 59 months over course the trial, this exclusion criteria will no longer be valid in subsequent MDA)
- Permanent disability or serious medical illness that prevents or impedes study participation and/or comprehension
- Pregnancy (screened for in women of child-bearing age [ages 12-45] using a pregnancy urine rapid test [e.g. SD Bioline hCG] the week prior to each MDA), as well as older females who have not yet had menopause
- Breast feeding if infant is within 1 week of birth
- Known allergy to ivermectin
- Possibility of *Loa loa* infection as assessed by travel history to Angola, Cameroon, Chad, Central African Republic, Congo, Democratic Republic of Congo, Equatorial Guinea, Ethiopia, Gabon, Nigeria, and Sudan.
- Enrolled in any other active clinical trials

Active case surveillance cohort exclusion criteria:

- Residence outside of the study site
- Permanent disability, serious medical illness that prevents or impedes study participation

---

Additional PK/PD cohort exclusion criteria:

- Concurrent use of drugs known to interfere with CYP3A4 metabolism within the past 14 days. (Section 6.6)
- Hemoglobin < 7g/dL

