#### 10.4. **Final Analysis Plan**

The final statistical plan will be written in detail in the finalized standard operating procedure, before the start of the intervention phase, to ensure that the sampling plan (e.g. number of nurse visits, number of mosquitoes and blood samples) collected are appropriate for the intended analyses. In general, standard, two-tailed statistical hypothesis testing  $\alpha=0.05$ , as well as estimating and comparing the effect sizes and confidence intervals, will be used to measure the differences in entomological and parasitological secondary outcomes between arms. The tests used will depend on the type of data collected (e.g., survivorship of blood fed mosquitoes in each arm per collection interval, proportion of mosquitoes parous/arm per collection interval, average counts of trophozoites/slide or counts of the parasite molecular force of infection, sporozoite rates in mosquitoes), and their distributions. These data will also be used to make generalized linear and non-linear mixed effects models in R, SAS or other programs to understand the functional relationships of measured entomological and parasitological variables and the relative contributions of various independent variables on variation in the dependent variable.

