2.1.2 Definition of primary efficacy endpoint

A malaria episode is defined as the presence of a temperature of ≥37·5°C and/or history of fever in the last 24 hours, along with a positive rapid diagnostic test (RDT) for *Plasmodium* species (any species).

A participant's time-at-risk will be considered as censored for 14 days following a diagnosis and treatment of malaria due to the impacts of treatment on risk of recurrent malaria. Person time will be defined in 7-day consecutive intervals, with one or more visits occurring during this time considered as an eligible person-week.

Eligibility for MDA is determined at the beginning of each intervention season and is retained for the remainder of that season.

- Newborns are eligible for inclusion and will be considered exposed beginning at the time of their 1st ACD visit.
- Children who turn 11 years of age during an intervention season will remain eligible for the ACD cohort for the remainder of that season.
- If a participant ages out of ACD cohort in the first season, they will not be eligible for the ACD cohort in the second season.
- Eligibility for SMC is determined by the MoH community workers, not by the RIMDAMAL II study team. Participants may age out of SMC (>59 months) in the 1st season and become eligible for MDA (≥90 cm and >59 months) in the second season. They will not become eligible for MDA during the season where this occurred.

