2.1.3 Analysis methods for primary endpoint

Primary efficacy analysis:

• Intention-to-treat analyses will include the assigned treatment arms and results from all clusters. Incidence rates will be determined using a Poisson regression that models

counts of malaria episodes and includes an offset that accounts for log person-weeks. This yields a malaria rate per week per child per rainy season for intervention and control villages (averaged across year 1 and 2).

- The estimate for the primary analysis is the exponentiated beta coefficient for the treatment covariate across both seasons. This rate ratio corresponds to the difference in rates between treatment and control villages.
- Statistical Model:
 - The model below shows the outcome (malaria episodes), a coefficient for treatment group (intervention vs control), a coefficient for year (rainy season 1 vs rainy season 2), a coefficient for sex, an offset term to account for person-weeks, and a random effect to account for clustering at the village level.

Let Y_{hijk} be the number of malaria episodes for subjects k within village j within treatment i within year h

```
\begin{split} \log(Y_{ijk}) &= \alpha + \beta_1 X_i + \beta_2 X_{ijk} + \beta_3 X_{hijk} + \log(t_{hk}) + u_{ij} \\ \text{where } X_i &= 0 \text{ (control) or } X_i &= 1 \text{ (Ivermectin)}, \ X_{ijk} &= 0 \text{ (female) or } X_{ijk} &= 1 \text{ (male) and} \\ X_{hijk} &= 1 \text{ (Year 1) or } X_{hijk} &= 2 \text{ (Year 2) and:} \\ & \alpha &= \text{ Intercept} \\ & \beta_1 &= \text{ Log of the rate ratio treatment vs control} \\ & \beta_2 &= \text{ Log of the rate ratio males vs females} \\ & \beta_3 &= \text{ Log of the rate ratio Year 1 vs Year 2} \\ & \log(t_{hk}) &= \text{ Denotes log person-weeks} \\ & u_{ij} &= \text{ Denotes the random village effect} \end{split}
```

- Detailed simulation studies were used to determine the appropriate analysis procedure for this trial (Jackson, et al. *Trials* 2021)
- Software:
 - SAS v9.4 (SAS Institute Inc., Cary, NC) will be used for the primary statistical analyses.
 - A Kenward Roger degrees of freedom correction will be applied to account for the limited number of clusters
 - Code Example:

```
proc glimmix data=WORK.DataExample;
class Village_code Treatment YEAR Sex;
Model Episodes = Treatment Year Sex/ s dist=Poisson ddfm=kr offset =
InPersonWeeks;
Random INT / subject= Village_code;
Run:
```

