2.3.3 Subgroup analysis

- **2.3.3.1** SMC-treated children only incidence will be compared between those children who received SMC only (age 3-59 months)
- 2.3.3.2 IVM/placebo-treated children only incidence will be compared between those children who received MDA/placebo only (≥90 cm and ≤10 y/o)

Other notes regarding covariates/effects to consider:

 Analyze the IRs by cluster and arm over short time periods (by week) for each season using regression approaches

- Malaria transmission intensity naturally varies over each season due to changing weather and mosquito vector species and densities and changing human immunity.
- Each of the 4 ivermectin MDAs per season acts like a "pulse" of insecticidal blood that starts high and then the mosquito-killing efficacy wanes over time as the ivermectin is eliminated from treated persons' blood. We estimate the mosquito killing activity lasts for 2-3 weeks but is highest in the week after the MDA is given. On top of this, there would be a time delay, as the killing would reduce biting, and then a week to 2 later, the numbers of parasitemic individuals would decrease
- Spatial effects between and within clusters
 - The incidence difference based on child/ HH location in cluster inner vs. outer edge of the cluster
 - Differences based on the density of non-study populations nearby (within several km of the cluster boundaries)
- Random effect within HHs in clusters (due to HH size, proportion of males to females in a HH, age proportion in a HH proportion, HH members treated and/or treated over time)

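### Subgroup incidence analyses use strata defined by treatment received, no written model for them, and an MDA eligibility rule that differs between SAP and protocol

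*SAP*

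**What the plan says.** **Subgroups and covariates.** SAP 2.1 says: "Subgroup analyses will include an evaluation of fixed effects such as LLIN use, age, and treatment with SMC or IVM". It promises intervention-effect estimates with 95% confidence intervals from the subgroup analyses as well as the primary analysis. SAP 2.3.3, within the tertiary and exploratory part, defines one stratum as children who received SMC. For the other, "incidence will be compared between those children who received MDA/placebo only". For adverse events, SAP 2.2.1 uses receipt of SMC for one child group and a mixture of MDA eligibility and receipt for the other. A subgroup table is among the main manuscript tables in SAP 3.

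**Model.** The only incidence model written out is the primary one in SAP 2.1.3: Poisson, with arm, year and sex as fixed effects, a person-week offset, and "a random effect to account for clustering at the village level". It has no child, household or overdispersion term. SAP 2.3.3 mentions a household random effect only in its notes of effects to consider.

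**Eligibility.** SAP 2.1.2 says: "Eligibility for MDA is determined at the beginning of each intervention season and is retained for the remainder of that season". It adds that a child who ages out of SMC during a season does not become eligible for MDA in that season. Protocol 5.2 says of the height exclusion, and again of the SMC exclusion, that once the child has outgrown it "this exclusion criteria will no longer be valid in subsequent MDA".

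**The concern.** The contrast between children old enough for MDA and children on SMC, who can benefit only indirectly, is central to explaining how the intervention works. Three features weaken it.

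1. Receipt can depend on tolerability and compliance. Protocol 5.3.3 lists suspected allergic reaction and noncompliance as grounds for stopping product. Under Protocol 2.2, caregivers give the second and third daily doses at home. The SAP does not say how many rounds or doses count as received. For adverse events, the event itself may end receipt.
2. A fixed effect for IVM treatment beside arm would split the randomised effect in two.
3. Age, net use and SMC or MDA status vary within villages. A village intercept does not absorb child or household differences in their standard errors.

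A false lead about who benefits could then reach a main table.

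**Working it through.** **Step 1: the plan's own figure.** Protocol 10.2 gives "1.088 malaria episodes/child/year and 0.619 malaria episodes/child/year" for control and intervention. With between-cluster CV 0.258, 48 children per cluster (taken as 48 child-years), and two-sided α 0.05 (Protocol 10.4 specifies "standard, two-tailed statistical hypothesis testing"), the unmatched rate formula is

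c = 1 + (z_α/2 + z_β)² [(λ0+λ1)/y + k²(λ0²+λ1²)] / (λ0−λ1)²

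= 1 + 7.849 × [1.707/48 + 0.06656 × 1.5669] / 0.21996 = 5.99.

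This reproduces the 6 clusters per arm that "is necessary to detect a significant difference in the rates between the arms with 80% power". At 7 × 100 children and the same k, power is 90.9%. The design inputs are sound and are used below.

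**Step 2: IVM receipt beside arm.** Write log rate = α + β·arm + γ·(received IVM). The receipt term is always 0 in the control arm. With share p of active-arm person-time in receivers, the total rate ratio is

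RR = exp(β) × [(1−p) + p·exp(γ)].

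So exp(β) compares active-arm children who did not take IVM with all control children. It equals the total RR only if γ = 0 or p = 0. As an illustration with assumed p = 0.5 and the planned RR of 0.569:
- exp(γ) = 0.8 gives a bracket of 0.9 and exp(β) = 0.569/0.9 = 0.632.
- exp(γ) = 1.25 gives a bracket of 1.125 and exp(β) = 0.569/1.125 = 0.506.

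**Step 3: standard errors if the village-only model is reused.** The documents give no child or household variance, so it is assumed here. Simulated trials had 14 villages × 100 children, 20 households of 5 per village, village CV 0.258, the planned rates over two child-years, gamma child and household effects, and covariate prevalence 50%. There were 4,000 trials per setting. A Poisson score test conditional on village stood in for the village-only mixed model. Rejection at nominal 5% for a covariate with no effect:

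| Child CV | Household CV | Child-level covariate | Household-level covariate |
|---|---|---|---|
| 0 | 0 | 5.4% | 5.3% |
| 0.3 | 0 | 7.2% | 6.8% |
| 0.5 | 0 | 10.9% | 9.8% |
| 1.0 | 0 | 24.8% | 26.2% |
| 0 | 0.3 | 6.9% | 15.3% |
| 0.5 | 0.3 | 12.2% | 21.1% |
| 0.7 | 0.5 | 22.8% | 36.6% |

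Arm-by-covariate contrasts ran from 9.6% (child CV 0.5, child-level covariate) to 33.6% (child 0.7 plus household 0.5, household-level covariate).

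Hand check for a child-level covariate: the variance is inflated by D = 1 + CV² × m, where m is the event-weighted expected count per child. Here m = (2.176² + 1.238²)/(2.176 + 1.238) × (1 + 0.258²) = 1.96. CV 0.5 gives D = 1.49 and P(|Z| > 1.96/√1.49) = 10.8%. CV 1.0 gives D = 2.96 and 25.5%. Both agree with the table. With a lower assumed burden of 0.7 episodes per child-season (m = 1.4), CV 1.0 gives D = 2.4 and 20.6%, hence the range of 21-25%.

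The result depends on exposure. If the rates are annual and only the two four-month follow-up periods count, expected counts are one third as large (m = 0.65). The same formula then gives 6.9% at CV 0.5 and 12.7% at CV 1.0.

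**Step 4: what is not affected.** The arm effect inside a 50-child-per-village stratum was tested with a village intercept and t on 12 df, over 800 null trials per setting. Type I error was 4.0% to 5.9%; the Monte Carlo standard error is √(0.05 × 0.95/800) = 0.8 points. The whole-cohort treatment test gave 4.5% to 5.2%.

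**Step 5: a method that holds its level.** Using the spread of village-specific log rate ratios (t on 13 df for a covariate effect, 12 df for arm by covariate) gave 4.3% to 6.1% in every setting tried.

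**Step 6: size of the eligibility conflict.** Assume 100 children per village spread evenly over eleven single years of age (0 to 10), about 9.1 per year. Over three to four months, 2.3 to 3.0 children per village pass 60 months. That is 2-3% of the cohort and 4-6% of the 54.5 children aged 5 to 10. Children who pass 90 cm mid-season are not counted.

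**The case against.** Several stronger readings are tempting, and the documents do not support them.

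- **That the plan commits subgroup analyses to a village-only model.** The SAP ties that model to the primary analysis, and SAP 2.3.3 lists a household effect to consider. What stands is that the model is unspecified and the only one on paper does not suit these effects. The SAP's future-work appendix names village and household random effects for the parasite-genotype counts, beside the same covariates.
- **That subgroup intervals are generally too narrow.** The estimate SAP 2.1 promises is the intervention effect, and within a single stratum it holds its level. Only covariate effects and contrasts between strata are exposed.
- **That the receipt-based strata are biased.** The trial is masked and placebo-controlled, and Ministry of Health workers decide SMC eligibility. Bias in the arm contrast needs receipt to differ by arm, for example through tolerability. That is possible, not demonstrated. SAP 2.3.3 also attaches age or height bounds to the strata.
- **That IVM receipt will certainly sit beside arm.** SAP 2.3.3 describes an IVM/placebo group, which exists in both arms. SAP 2.1 nevertheless names IVM alone as a fixed effect, so the wording needs settling.
- **That pregnancy screening moves children between strata.** It starts at age 12 and does not touch children up to 10.

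The analyses are also exploratory, with no α claimed. That limits the consequence but does not remove it, given the planned main table.

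**Conclusion.** The point holds in a limited form. Strata defined by receipt give up part of the protection of randomisation for no gain, since age and height eligibility can be used instead. IVM receipt beside arm, if that is meant, changes what the arm coefficient estimates; this follows from algebra and needs no variance assumption.

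The inflation of type I error is conditional on two things: reuse of the village-only model, and child or household variation that the documents do not quantify. With none there is no inflation. The tests were close stand-ins, and the SAP's SAS procedure was not run. The primary analysis is not in question.

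The eligibility passages do contradict each other. The effect on the strata is small under the even-age assumption, and smaller still while the strata rest on receipt. It becomes relevant once they rest on eligibility.

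**What to change.** 1. Define the SMC and MDA strata, for incidence and for adverse events in children, by age and height eligibility rather than receipt.
2. Do not enter IVM receipt as a covariate in any model that contains arm, and reword SAP 2.1 accordingly.
3. Write out the model for covariate effects and arm-by-stratum contrasts: an arm-by-stratum term, child and household variation, and a village-by-stratum random effect. Alternatively, use village-level summaries with t tests. A child intercept alone would not cover household-level covariates such as net use.
4. Reconcile SAP 2.1.2 with Protocol 5.2 on when MDA eligibility is assessed, and derive the strata from the single reconciled rule.

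The cost is SAP wording and a little more modelling. Intervals for these exploratory contrasts will be somewhat wider, and eligible but untreated children will dilute the strata slightly. No new data are needed.
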